6.14.3. Lilly Subgroup Identification

CCI

6.15. Protocol Deviations

Protocol deviations will be identified throughout the study. Important protocol deviations are defined as those violations from the protocol likely to have a significant impact on the completeness, accuracy, and/or reliability of the study data or that may significantly affect a subject's rights, safety, or well-being.

[Table RHBV.6.12](#) includes the categories and subcategories of important protocol deviations, whether or not these deviations will result in the exclusion of patients from PPS, the source of identification for the deviations, and the statistical programming guidance for the CSR.

The number and percentage of patients having important protocol deviations (s) will be summarized within category and subcategory of deviations by treatment group for:

- Period 2 (ITT Population);
- Period 3 (Extended Treatment Period Population).

A by-patient listing of important protocol deviations will be provided.

Table RHBV.6.12. Identification and Action of Important Protocol Deviations

Important Protocol Deviation Category/Subcategory/Study Specific	Action for PPS Analysis	Source to Identify Protocol Deviation ^a
Category: Eligibility		
Subcategory: Inclusion/Exclusion		
[1] No established diagnosis of rad-axSpA at screening	Exclude from PPS	Monitor and Stats
[2] History of back pain <3 months or age at onset ≥45 years	Exclude from PPS	Monitor and Stats
[3] No active rad-axSpA defined as BASDAI ≥4 and total back pain ≥4 on an NRS at screening and baseline	Exclude from PPS	Monitor and Stats
[4] Not have had an inadequate response to 2 or more NSAIDs at therapeutic dose range for a total duration of at least 4 weeks AND not have history of intolerance to NSAID (for Japan patients, not have had NSAID or had 1 NSAID for a duration of less than 12 weeks)	Exclude from PPS	Monitor
[5] Not have a history of prior therapy for axSpA of at least 12 weeks prior to screening	Exclude from PPS	Monitor
[6] Not have stable dose for NSAID or COX-2 for at least 2 weeks prior to baseline randomization, if taking NSAID or Cox-2 inhibitors	Exclude from PPS if 1. Stopped or decreased dose for a current med <3 days before randomization; or 2. Increased dose for a current med or started a new med <2 wks before randomization.	Monitor and Stats
[7] Not ≥18 years of age at time of screening; or <20 years of age for patients from Taiwan sites	Exclude from PPS	Monitor and Stats
[8] Female patient of childbearing potential with positive pregnancy test; or did not use a reliable method of birth control, if applicable	Do not exclude from PPS	Monitor and Stats
[10] Have total ankylosis of the spine at screening	Exclude from PPS	Monitor
[11] Have any condition or contraindication as addressed in the local labeling for adalimumab	Exclude from PPS	Monitor
[12] Have a history of other systemic inflammatory diseases or other chronic pain conditions that might confound the evaluations of benefit from ixekizumab therapy	Exclude from PPS	Monitor
[13] Have active Crohn's disease (CD) or active ulcerative colitis (UC) at screening	Do not exclude from PPS	Monitor and Stats

Important Protocol Deviation Category/Subcategory/Study Specific	Action for PPS Analysis	Source to Identify Protocol Deviation^a
[14] Have evidence of active anterior uveitis (an acute episode) within the last 4 weeks prior to baseline randomization.	Do not exclude from PPS	Monitor and Stats
[15] Have current or a history of lymphoproliferative disease, or signs or symptoms of lymphoproliferative disease; or have active or history of malignant disease within 5 years prior to Visit 2	Do not exclude from PPS	Monitor
[16] Have had fluid overload, MI or new onset ischemic heart disease, uncompensated heart failure, or other serious cardiac disease within 12 weeks prior to Visit 2	Do not exclude from PPS	Monitor
[17] Presence of significant, uncontrolled cerebro-cardiovascular events at screening	Do not exclude from PPS	Monitor
[18] Presence of respiratory, hepatic, renal, gastrointestinal, endocrine, hematologic disorder at screening that pose unacceptable risk to patient or interfering with interpretation of data	Do not exclude from PPS	Monitor
[19] Presence of neurologic or neuropsychiatric disorders at screening that pose unacceptable risk to patient or interfering with interpretation of data	Do not exclude from PPS	Monitor
[20] Presence of significant uncontrolled neuropsychiatric disorder, recent history (30 days prior to V1 and anytime between V1 and V2) of a suicide attempt, have a score of 3 on Item 12 (Thoughts of Death or Suicide) of the QIDS-SR16 at Visit 1 or Visit 2, or at risk for suicide	Do not exclude from PPS	Monitor and Stats
[21] Have presence or personal history or family history (1st degree relative) of demyelinating disorder.	Exclude from PPS	Monitor
[22] In the past 12 weeks prior to V2, had a serious infection, hospitalization or IV antibiotics for an infection; in the past 24 weeks prior to V2, had a serious bone or joint infection, ever had an infection of an artificial joint, or infection that occurs with increased incidence in an immunocompromised host. Japan patients with a positive beta-D-glucan test at screening and a confirmed diagnosis of PCP	Do not exclude from PPS	Monitor
[23] Have a known immunodeficiency or are immunocompromised to an extent such that participation in the study would pose an unacceptable risk to the patient	Do not exclude from PPS	Monitor
[24] Have or had a herpes zoster or any other clinically apparent varicella-zoster virus infection within 12 weeks of Visit 2	Do not exclude from PPS	Monitor
[25] Have any other active or recent infection within 4 weeks of Visit 2 that would pose an unacceptable risk to the patient	Do not exclude from PPS	Monitor
[26] Have known allergy to rubber or latex.	Do not exclude from PPS	Monitor

Important Protocol Deviation Category/Subcategory/Study Specific	Action for PPS Analysis	Source to Identify Protocol Deviation^a
[27] Have a known allergy or hypersensitivity to any biologic therapy that would pose an unacceptable risk to the patient if participating in this study	Exclude from PPS	Monitor
[28] Have had surgical treatment of a joint to be assessed in the study within 8 weeks prior to baseline randomization or will require such during the first 16 weeks of the trial	Exclude from PPS depending on the clinical significance	Monitor
[29] Had any major surgery within 8 weeks prior to Visit 2, or will require such during the study that would pose an unacceptable risk to the patient	Do not exclude from PPS	Monitor
[30] Have received cDMARDs, and/or other therapies such as but not limited to: gold salts, cyclosporine, azathioprine, dapsons, 6-mercaptopurine, mycophenolate mofetil, or any other immunosuppressive agents within 4 weeks prior to baseline randomization.	Exclude from PPS if 1. Stopped or decreased dose for a current med ≤ 3 days before randomization; or 2. Increased dose for current med or started a new med < 4 wks before randomization. Patients with Combo cDMARD drug use will be removed from PPS	Monitor and Stats
[31] Current use of oral corticosteroids > 10 mg/day prednisone or its equivalent	Exclude from PPS if 1. dose > 10 mg/day any time within 4 weeks; or 2. Stopped or decreased dose for a current med < 10 days before randomization; or 3. Increased dose for current one or started a new one < 4 wks before randomization;	Monitor and Stats
[32] Have received any prior, or are currently receiving, treatment with biologic or other immunomodulatory agents, including investigational therapies (such as but not limited to Janus kinase (JAK) inhibitors, TNF inhibitors, IL-1, IL-6, IL-23, IL-17 (including ixekizumab), IL-17R, T cell, or B cell targeted therapies).	Exclude from PPS	Monitor and Stats
[33] Are currently enrolled in, have participated, or discontinued from a clinical trial involving an investigational product or nonapproved use of a drug or device within the last 30 days prior to screening or a period of at least 5 half-lives of the last administration of the drug, whichever is longer	Exclude from PPS	Monitor

Important Protocol Deviation Category/Subcategory/Study Specific	Action for PPS Analysis	Source to Identify Protocol Deviation^a
[34] Are currently enrolled in any other clinical trial involving an investigational product or any other type of medical research judged not to be scientifically or medically compatible with this study	Exclude from PPS	Monitor
[35] Are currently receiving or have received treatment with denosumab within 6 months prior to baseline randomization.	Do not exclude from PPS	Monitor and Stats
[36] Have received any parenteral glucocorticoid administered by intra-articular, intramuscular, or IV injection within 6 weeks prior to baseline randomization, or a parenteral injection of glucocorticosteroids is anticipated during the Period 2.	Exclude from PPS	Monitor and Stats
[37] Use of any opiate analgesic at average daily doses >30 mg/day of morphine or its equivalent or use of variable doses of any opiate analgesic within 6 weeks prior to baseline randomization. For Japan patients, Use of pregabalin >300 mg/day or use of variable doses of pregabalin within 2 weeks prior to baseline randomization.	Exclude from PPS If 1. doses >30 mg/day any time within 6 weeks before randomization; or 2. Stopped or decreased dose for a current one <7 days before randomization; or 3. Increased dose for current one or started a new one <6 wks before randomization	Monitor and Stats
[38] Had a live vaccination or participated in a vaccine clinical study within 12 weeks prior to Visit 2, or intend to have a live vaccination during the study or within 12 weeks of completing study treatment	Do not exclude from PPS	Monitor
[39] Had a vaccination with BCG within 12 months prior to Visit 2, or intend to have this vaccination with BCG during the study or within 12 months of completing study treatment	Do not exclude from PPS	Monitor and Stats
[40] Have a body temperature $\geq 38^{\circ}\text{C}$ (100.5°F) at Visit 2	Do not exclude from PPS	Monitor and Stats
[41] Have evidence or suspicion of active or latent TB	Do not exclude from PPS	Monitor
[42] Are positive for human immunodeficiency virus serology (HIV)	Do not exclude from PPS	Monitor and Stats
[43] Have evidence of or test positive for hepatitis B virus (HBV) and are HBV DNA positive	Do not exclude from PPS	Monitor and Stats
[44] Have evidence of or test positive for hepatitis C virus (HCV)	Do not exclude from PPS	Monitor and Stats
[45] Have ECG abnormalities that are considered clinically significant and would pose an unacceptable risk to the patient if participating in the study	Do not exclude from PPS	Monitor
[46] Patients having contraindications to MRI	Do not exclude from PPS	Monitor

Important Protocol Deviation Category/Subcategory/Study Specific	Action for PPS Analysis	Source to Identify Protocol Deviation^a
[47] At Visit 1, have a neutrophil count <1.50 GI/L	Do not exclude from PPS	Monitor and Stats
[48] At Visit 1, have a lymphocyte count <0.80 GI/L; for Japan patients, lymphocyte count <1.0 GI/L)	Do not exclude from PPS	Monitor and Stats
[49] At Visit 1, have a platelet count <100 GI/L	Do not exclude from PPS	Monitor and Stats
[50] At Visit 1, have aspartate aminotransferase (AST) or alanine aminotransferase (ALT) >2.5 times the upper limit of normal (ULN)	Do not exclude from PPS	Monitor and Stats
[51] At Visit 1, have a total white blood cell (WBC) count <3.00 GI/L; for Japan patients, WBC count <4.0 GI/L)	Do not exclude from PPS	Monitor and Stats
[52] At Visit 1, have hemoglobin <8.5 g/dL for male patients and <8.0 g/dL for female patients	Do not exclude from PPS	Monitor and Stats
[53] Have other clinical laboratory test results at Visit 1 that are outside the normal reference range for the population and are considered clinically significant	Do not exclude from PPS	Monitor
[54] Have donated >450 mL of blood within the last 4 weeks prior to Visit 1, or intend to donate blood during the course of the study	Do not exclude from PPS	Monitor
[55] Are women who are lactating or breastfeeding	Do not exclude from PPS	Monitor
[56] Are investigator site personnel directly affiliated with this study and/or their immediate families	Exclude from PPS	Monitor
[57] Are Lilly employees or its designee or are employees of third-party organizations (TPOs) involved in the study	Exclude from PPS	Monitor
[58] Are unwilling or unable to comply with the use of a data collection device to directly record data from the patient,	Exclude from PPS when occurred in Period 2	Monitor
[59] Have any other condition that precludes the patient from following and completing the protocol	Exclude from PPS	Monitor
Subcategory: other		
Rescreened patients were enrolled but did not meet rescreening criteria per protocol	Do not exclude from PPS	Monitor
Category: Study Procedures		
Subcategory: Violation of Discontinuation Criteria		
[D1] Lilly medical not consulted when patient met hepatic lab criteria for consideration of discontinuation	Do not exclude from PPS	Monitor

Important Protocol Deviation Category/Subcategory/Study Specific	Action for PPS Analysis	Source to Identify Protocol Deviation^a
[D2-N] Neutrophil counts <0.50 GI/L, or >=0.50 GI/L and <1.00 GI/L based on 2 test results within 1 week of knowing 1 st result, or >=1.00 GI/L and <1.50 GI/L based on 3 test results and a concurrent infection	Do not exclude from PPS	Monitor and Stats
[D2-W] Total WBC count <2.00 GI/L	Do not exclude from PPS	Monitor and Stats
[D2-L] Lymphocyte count <0.50 GI/L	Do not exclude from PPS	Monitor and Stats
[D2-P] Platelet count <50 GI/L	Do not exclude from PPS	Monitor and Stats
[D3] patient experiences a severe AE, an SAE, or a clinically significant change in a laboratory value that merits the discontinuation of the investigational product and appropriate measures being taken.	Do not exclude from PPS	Monitor
[D4] Clinically significant systemic hypersensitivity reaction does not respond to treatment	Do not exclude from PPS	Monitor
[D5] Patient became pregnant	Do not exclude from PPS	Monitor
[D6] Patient developed a malignancy (Patients may be allowed to continue if they develop no more than 2 nonmelanoma skin cancers during the study)	Do not exclude from PPS	Monitor
[D7] Enrolled in prohibited medical research	Exclude from PPS when occurred in Period 2	Monitor
[D9] Patient develops any condition or contraindication as addressed in the local labeling for adalimumab	Exclude from PPS when occurred in Period 2	Monitor
[D12] Lilly stopped the patient participation	Do not exclude from PPS	Monitor
[D13] Patient became HBV DNA positive	Do not exclude from PPS	Monitor
[D14] Patient has a confirmed diagnosis of PCP during the study for patients from Japan sites	Do not exclude from PPS	Monitor
Category: Study Procedures		
Subcategory: Excluded Con-meds	Exclude from PPS (Excluded Con-meds refers to clinically meaningful change in con-meds (Appendix 13) occurred during Period 2 and prescribed for primary study condition] Excluded Con-meds in Period 3 refer to the lists in Appendix 13	Monitor and Stats
Subcategory: Lab/Imaging Criteria		

Important Protocol Deviation Category/Subcategory/Study Specific	Action for PPS Analysis	Source to Identify Protocol Deviation^a
Missing imaging as per protocol schedule of events	Do not exclude from PPS	Monitor
Missing lab chemistry and hematology: missing baseline or not having at least 1 postbaseline	Do not exclude from PPS	Stats
Subcategory: Other		
Missing QIDS total score: missing baseline or any scheduled visit prior to discontinuation visit	Do not exclude from PPS	Stats
Missing Columbia scale at any visit except Visit 1	Do not exclude from PPS	Monitor and Stats
Missing ASAS components for ASAS40 derivation: not having Week 16 measurement for patients who have completed Week 16	Do not exclude from PPS. Note: if missing ASAS components lead to missing ASAS40, such patient will be treated as nonresponder for the Week 16 ITT analyses	Stats
Had unqualified site personnel perform clinical safety and/or efficacy assessments	Do not exclude from PPS	Monitor
Category: Investigational Product		
Subcategory: Treatment Assignment/Randomization Error		
Took incorrect study medication	Do not exclude from PPS. Analyze 'As randomized' or 'As assigned'.	Stats and monitor
Subcategory: Compliance	Exclude from PPS when occurred during Period 2	Stats
Subcategory: Patient took medication not fit for use	Do not exclude from PPS	Monitor
Subcategory: Other		
Randomized but did not take any study medication	Exclude from PPS	Stats
Category: Safety		
Subcategory: SAEs	Do not exclude from PPS	Monitor
Category: Informed Consent		
Subcategory: Informed Consent not Obtained/Missing/Late	Exclude from PPS	Monitor and Stats
Subcategory: Improper Informed Consent	Do not exclude from PPS	Monitor
Category: administrative/oversight		

Important Protocol Deviation Category/Subcategory/Study Specific	Action for PPS Analysis	Source to Identify Protocol Deviation ^a
Subcategory: Reg/Ethic Approvals	Exclude from PPS	Monitor
Subcategory: Other		
Enrolled in a site with significant GCP non-compliance issue	Exclude from PPS	Monitor

Abbreviations: AE = adverse event; axSpA = axial spondyloarthritis; ASAS = Assessment of Spondyloarthritis International Society;; BASDAI = Bath Ankylosing Spondylitis Disease Activity Index; BCG = Bacille de Calmette et Guérin; cDMARD = conventional disease-modifying antirheumatic drug; ECG = electrocardiogram; GCP = good clinical practice; IL = interleukin; ITT = intent-to-treat; IV = intravenous; NSAID = nonsteroidal anti-inflammatory drug; MI = myocardial infarction; NRS = numerical rating scale; PCP = pneumocystis pneumonia; PPS = per protocol set; QIDS-SR16 = Quick Inventory of Depressive Symptomatology–Self-Report 16 items; rad = radiographic; TB = tuberculosis; V = visit; WBC = white blood cell.

^a The term “Monitor” indicates the protocol deviation will be identified by site monitors and entered into monitor’s list using a spreadsheet. The spreadsheet will be exported as Study Data Tabulation Model (SDTM) DV domain.

The term “Stats” indicates the protocol deviation will be programmed based on data in clinical database by statistical programmers with the statistical programming guidance provided as the last column. The detailed programming specification will be documented in Analysis Data Model (ADaM) specification.

The terms “Monitor and Stats” indicates the protocol deviation will be a combination of monitor’s list (SDTM.DV domain) and statistical programming from clinical database, the deviation will show if either source identifies.

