#### **Prior/Concurrent Therapy or Clinical Trial Experience**

- [30] Have received cDMARDs and/or other therapies such as but not limited to: gold salts, cyclosporine, azathioprine, dapsone, 6-mercaptopurine, mycophenolate mofetil, or any other immunosuppressive agents within 4 weeks prior to baseline randomization.

Exception: MTX (oral or parenteral up to 25 mg/week), sulfasalazine (up to 3 g/day), or hydroxychloroquine (up to 400 mg/day) may be allowed IF at stable dose for at least 4 weeks prior to baseline randomization.

AND

if used, must not be in any combination with other cDMARDs.

**Note:** If MTX is used, local standard of care is to be followed for concomitant administration of folic or folinic acid with MTX.

- [31] Use of oral corticosteroids  $>10$  mg/day prednisone or its equivalent.
- Note:** If patients are taking prednisone or its equivalent and the dose is  $\leq 10$  mg/day, the dose must be stable for at least 4 weeks prior to baseline randomization.
- [32] Have received any prior, or are currently receiving, treatment with biologic or other immunomodulatory agents, including investigational therapies (such as but not limited to Janus kinase (JAK) inhibitors, TNF inhibitors, IL-1, IL-6, IL-23, IL-17 (including ixekizumab), IL-17R, T cell, or B cell targeted therapies).

[33] Are currently enrolled in, have participated, or discontinued from a clinical trial involving an investigational product or nonapproved use of a drug or device within the last 30 days prior to screening or a period of at least 5 half-lives of the last administration of the drug, whichever is longer.

**Note:** Investigational products that are biologic or other immunomodulatory agents are not permitted regardless of washout period (described in criterion above).

[34] Are currently enrolled in any other clinical trial involving an investigational product or any other type of medical research judged not to be scientifically or medically compatible with this study.

[35] Are currently receiving or have received treatment with denosumab within 6 months prior to baseline randomization.

[36] Have received any parenteral glucocorticoid administered by intra-articular, intramuscular, or IV injection within 6 weeks prior to baseline randomization, or for whom a parenteral injection of glucocorticosteroids is anticipated during the Blinded Treatment Dosing Period (Period 2) of the study.

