6.1.5. Analysis Populations

The following major analysis populations will be used (additional analysis populations for specific analysis will be defined in the corresponding analysis section):

Intent-to-Treat Population (ITT Population): Unless otherwise specified, efficacy and health outcomes analyses for Period 2 will be conducted on the ITT Population, defined as all randomized patients, even if the patient does not take the assigned treatment, does not receive the

correct treatment, or otherwise does not follow the protocol. Patients will be analyzed according to the treatment to which they were assigned.

Per-Protocol Set (PPS): In addition, the primary efficacy analysis will be repeated using the PPS, which is defined as all randomized patients who are compliant with therapy, who do not have a subset of important protocol deviations that impact the primary efficacy endpoint (Section 6.15), and whose investigator site does not have significant good clinical practice (GCP) issues that require a report to the regulatory agencies prior to Week 16 (Visit 8). Compliance with therapy is defined to be missing no more than 20% of expected doses, not missing 2 consecutive doses (all injections at an injection week are counted as 1 dose), and not have any occurrence of over-dosing (that is, took more injections at the same time point than specified in the protocol) during Period 2.

Patients will be analyzed according to the treatment to which they were assigned.

Safety Population: Safety analyses for Period 2 will be conducted on the Safety Population, defined as all randomized patients who received at least 1 dose of study treatment. Patients will be analyzed according to the treatment to which they were assigned in that period.

Extended Treatment Period Population: Efficacy, health outcomes, and safety analyses for Period 3 will be conducted on the Extended Treatment Period Population, defined as all patients who received at least 1 dose of ixekizumab treatment during Period 3.

Adalimumab Washout Population: Treatment-emergent adverse event analyses for Period 3 from Week 16 to Week 20 will be conducted on the Adalimumab Washout Population, defined as all patients who were randomized to adalimumab at Week 0 and took at least 1 placebo dose from Week 16 through Week 20.

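### SAP Table RHBV.6.12 row [30] has no per-protocol trigger for stable single-agent use of a prohibited immunosuppressant, or for a permitted cDMARD above the protocol's cap

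*SAP*

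**What the plan says.** - **Eligibility.** Protocol Section 5.2, exclusion [30], rules out patients who received cDMARDs or other therapies, including "azathioprine, dapsone, 6-mercaptopurine, mycophenolate mofetil, or any other immunosuppressive agents within 4 weeks prior to baseline randomization". The exception covers methotrexate up to 25 mg/week, sulfasalazine up to 3 g/day or hydroxychloroquine up to 400 mg/day, at a dose stable for at least 4 weeks and not combined with another cDMARD. Protocol Section 6.8 repeats these caps for all periods.
- **PPS definition.** SAP Section 6.1.5 removes patients with a "subset of important protocol deviations that impact the primary efficacy endpoint" and refers to Section 6.15. The action column of Table RHBV.6.12 therefore decides who leaves.
- **Row [30] action.** There are three triggers: "Stopped or decreased dose for a current med" at most 3 days before randomization; "Increased dose for current med or started a new med" less than 4 weeks before; and "Patients with Combo cDMARD drug use will be removed from PPS".
- **Neighbouring rows.** Row [31] first excludes an oral corticosteroid dose above 10 "mg/day any time within 4 weeks". Row [37] first excludes an opiate dose above 30 "mg/day any time within 6 weeks before randomization". Both then add triggers for stops, decreases, increases and starts like those in row [30].
- **Period 2 medication row.** "Excluded Con-meds refers to clinically meaningful change in con-meds", with Appendix 13 cited for the detail.

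**The concern.** The eligibility rule concerns receipt of the drug, and a stable dose excuses only the three named agents within their caps. The PPS action concerns mainly timing and change. The two therefore part company for a patient who takes one prohibited agent, or too much of a permitted one, without altering it.

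The outcome runs against the purpose of the PPS. A patient whose permitted methotrexate was raised within the cap three weeks before entry is removed. A patient who takes a prohibited immunosuppressant unchanged up to randomization and on to Week 16 is kept. SAP Section 6.10.3 uses the PPS to support the primary ASAS40 result, and Table RHBV.6.5 also uses it for ASAS20. As written, neither analysis can show robustness to this kind of violation.

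**Working it through.** The plan gives no figure on this point, so the check is first one of logic and then of possible size.

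**Step 1: row [30] as a rule.** Exclude from the PPS if (1) a stop or decrease occurred 3 days or less before randomization, or (2) an increase or start occurred less than 28 days before, or (3) cDMARDs were combined.

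| Test patient | Trigger met | PPS |
|---|---|---|
| Azathioprine alone, unchanged for 200 days, ongoing | none | stays |
| Methotrexate 30 mg/week alone, unchanged for 200 days (cap 25) | none | stays |
| Azathioprine and methotrexate, both stable | 3 | removed |
| Azathioprine started 14 days before | 2 | removed |
| Azathioprine stopped 2 days before | 1 | removed |
| Permitted methotrexate raised 21 days before | 2 | removed |

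The first two patients violate exclusion [30] and are retained.

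**Step 2: could another row remove them?**
- Excluded Con-meds, for Period 2, requires a change. Unchanged use is not one on the visible wording.
- Row [23] (immunodeficiency or immunocompromise) is marked as not excluded from the PPS.
- Row [32] covers biologic and other immunomodulatory agents and bars any prior use. If it also covered conventional immunosuppressants, the 4-week window in [30] would have no function.

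**Step 3: possible size.** The inputs are 80 patients per arm and planned ASAS40 rates of 44% and 16% (SAP Section 5.3). In whole patients that is 0.44 × 80 ≈ 35 and 0.16 × 80 ≈ 13. Assume k = 1 or 3 affected patients in an arm. If x responders are removed among them, the rate becomes (r − x)/(80 − k).

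| Arm | k | All removed are nonresponders | All removed are responders |
|---|---|---|---|
| Ixekizumab, 35/80 = 43.75% | 1 | 35/79 = 44.30% (+0.55) | 34/79 = 43.04% (−0.71) |
| Ixekizumab | 3 | 35/77 = 45.45% (+1.70) | 32/77 = 41.56% (−2.19) |
| Placebo, 13/80 = 16.25% | 1 | 13/79 = 16.46% (+0.21) | 12/79 = 15.19% (−1.06) |
| Placebo | 3 | 13/77 = 16.88% (+0.63) | 10/77 = 12.99% (−3.26) |

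Across the all-or-none cases shown, one arm's rate moves by about 0.2 to 3.3 points.

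**The case against.** **Stable background therapy may be harmless.** The PPS is not meant to drop every eligibility violator; many rows are kept in, including denosumab [35]. Row [6] also works by change alone. Protocol Section 2.1 says axSpA responds poorly to cDMARDs. Removing changes and keeping stable use could therefore be deliberate. This does not explain row [30], which itself removes stable combination use. The same sentence of Section 2.1 covers systemic corticosteroids, yet row [31] removes stable over-cap corticosteroid use. The SAP gives no reason for treating a single prohibited agent differently.

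**Unseen text.** Appendix 13 is redacted, and the revision history says that programming guidance was moved to an external document. Either might contain a rule that catches these patients. That caveat stands. The visible Period 2 wording concerns change, however, and the Version 3 history entry describes prohibited medications as added to Appendix 13 for the extension period.

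**Stronger readings that the documents do not support.**
- A reader might infer that row [30] removes nothing but dose changes. It also removes recent starts, recent stops and combination cDMARD use.
- A reader might count a prohibited drug stopped 4 to 27 days before entry as part of the same gap. Rows [6], [30], [31] and [37] all use a shorter look-back for stops and decreases (3, 3, 10 and 7 days) than for starts and increases, so this looks like a design choice.
- A reader might take 3 patients out of 80 as a shift of nearly 4 points. Removal also shrinks the denominator, and the maximum is 3.3.

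**Small consequence.** The PPS is supportive. Important deviations are tabulated by arm and listed by patient, so affected patients remain visible. Protocol Section 5 permits no eligibility waivers, so few are likely. All of this stands and limits the weight of the point.

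**Conclusion.** The gap is real on the visible text. Row [30] has no trigger for stable single-agent use of an agent that the protocol prohibits, or for a permitted cDMARD above its cap, although the parallel rows [31] and [37] exclude over-cap use. It is a written rule that works against the stated purpose of the PPS, and not merely missing detail.

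Its reach is limited to the supportive PPS analyses of ASAS40 and ASAS20; the ITT primary analysis is untouched. The 0.2 to 3.3 points rest on an assumed 1 to 3 affected patients in an arm of 80 and on the planned response rates. The upper end needs three affected placebo patients who are all responders. Nothing in the documents suggests imbalance between arms, and similar shifts in both arms would largely cancel in the treatment difference. The conclusion also assumes that the redacted appendix and the external programming guidance contain no rule that closes the gap.

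**What to change.** Add a first trigger to row [30], parallel to rows [31] and [37]. It would exclude from the PPS a patient who, at randomization, is still taking an agent not permitted by protocol exclusion [30], or who took a permitted cDMARD above the protocol's own cap at any time in the 4-week window. Keep the existing triggers for change and combination use and the short look-back for stops.

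The row [30] condition was last revised for Version 2, before unblinding, and Version 3 was approved after it. The PPS should therefore not be redefined silently. Report the modified set as a labelled supplementary PPS analysis of ASAS40 and ASAS20, with the number of affected patients in each arm. If Appendix 13 or the programming guidance already removes these patients, a cross-reference in row [30] is enough.

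The cost is one table line, its programming and the extra output; the row is already sourced from both monitors and statistical programming. The downside is that the PPS may lose a few patients.
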